**Background, Rationale and Context**

Effective control of chronic pain is a top priority in the United States, as approximately 10% of adults have severe chronic pain – most of which is chronic lower back pain (CLBP)(National Institute of Health Statistics, 2006). CLBP is the leading cause of job-related disability and missed work. However, despite the advances in neuroscience over the past 20 years, we still largely treat CLBP pain with opiate narcotics, much as was done in the Civil War. In addition to their high abuse liability and dependence potential (1), only 30–40% of chronic pain patients declare they receive satisfactory (>50%) relief from their pain through pharmacological treatment (59). 96% of chronic pain patients using opiates reported insufficient control of pain, and on average opiate-using pain patients have experienced CLBP for more than a decade (59). A 2012 study demonstrated that patients with chronic pain resort to non-medical use of prescription opiates at high rates. This abundant use and misuse of opiates is a developing crisis, with 4.3 million users in 2014 (1), over 40% of prescription drug overdoses in the United States attributable to opioid analgesics (2), and total societal costs exceeding an estimated \$55 billion (3). Of individuals who misuse opioids, 80 to 90% initiated after having a legitimate prescription (13, 14) and 81% endorse pain as their reason for non-medical prescription opioid use (NMPOU) (14). **Consequently there is a critical need for new, treatments that can treat pain and reduce reliance on opiates in individuals with chronic pain. The goal of this R21 proposal is to evaluate 2 novel non-invasive brain stimulation strategies to mitigate pain in CLBP patients that are currently taking chronic opiates or that are seeking an alternative to relieve pain.**

Evaluating rTMS as a new, non-pharmacological approach to treating pain in opiate using individuals. TMS is a non-invasive brain stimulation method that is currently FDA-approved for the treatment of major depressive disorder. Repeated trains of stimulation can cause long-term potentiating (LTP) or depressing (LTD) effects on cortical areas directly under the coil (approximately 2cm depth) as well as monosynaptic projections (15-19). Our group has previously demonstrated that LTP-like TMS to the dorsal prefrontal cortex (DPFC, a node in the Executive Control Network (ECN)) can decrease perceived pain as well as corresponding BOLD signal in the “Pain Network in healthy controls (7, 8, 30) and clinical populations (31-34). The Pain Network is an expansion of the Salience Network (SN; insula, dorsal anterior cingulate) which includes the thalamus and somatosensory cortex (4-6). The SN represents the attentional aspects of pain whereas the thalamus and somatosensory cortex represent somatic aspects of pain. The analgesic effects of DPFC TMS can be blocked by naloxone, an opiate antagonist, suggesting TMS-induced analgesia is opiate mediated (7, 8). [name] (Co-Investigator) was the first to demonstrate that when LTP-like DPFC rTMS was delivered in the postoperative recovery room, patients used less morphine in the hospital and required less

[figure not shown]

Figure 1. Dynamic Interaction of Core functional connectivity networks. Adapted from Lerman et al 2014 JAMA Psychiatry. The Salience Network (SN), Executive Control Network (ECN), and Default Mode Network (DMN) represent 3 Core neural networks in the brain which are dynamically coupled. During pain, the SN & DMN are positively correlated (red), whereas the SN & ECN are anticorrelated (negatively correlated, blue). The outcomes of these aims will allow us to investigate baseline networks dynamic in CLBP patients treated with or without opiates (which has never been done) and test the hypotheses that increasing activity in the ECN (LTP-like TMS; Aim 1), and decreasing activity in the DMN (LTD-like TMS) will dampen pain in CLBP patients. The acute effect of 16 days of TMS (interventional phase and maintenance phase) as well as 1&2 month durability will be assessed.

morphine long-term (9). **These data all suggest that LTP-like DPFC TMS is a promising candidate for treating pain (Strategy 1, Aim 1).** This study will be the first to merge these findings, aiming to investigate the effects of TMS in both chronic opiate users, and individuals that cannot find any alternative to help relieve their pain.

**An alternative strategy is to apply LTP-like stimulation to the somatomotor cortex (LTP-like MC rTMS (Strategy 2, Aim 2).** This strategy is based on our understanding of functional neural architecture, wherein the SN is modulated by 2 other core networks: the executive control network (ECN) and the default mode network (DMN) (Figure 1). As stated above, it is possible to attenuate activity in the SN through LTP-like TMS to the DPFC, a node in the ECN. It is also possible to attenuate the SN through LTP-like TMS to the somatomotor cortex (a node in the DMN) (Hanlon et al 2017). **The proposed study will be the first to employ a randomized, double-blind, sham-controlled design to parametrically evaluate the longitudinal effects of 12 days of rTMS, followed by 4 maintenance rTMS sessions, delivered to the DPFC (Aim 1) or the MC (Aim 2) on self-reported pain and the brain's response to pain. This will be done in a cohort of patients recruited from the community as well as Wake Forest University (WFU) clinics with chronic lower back pain that have not been able to find adequate pain relief, whether or not they are using prescription opiates for 3 or more months.**

The scientific rationale for rTMS effects on pain in CLBP patients. TMS is the only non-invasive tool available to directly activate a specific neural circuit in humans. Opiate dependent individuals have reduced functional connectivity (35) between regions of the Pain Network (e.g. dorsal anterior cingulate cortex [dACC], insula, and thalamus (4-6, 36)) and the ECN (e.g. DPFC (37)). Previous TMS studies have demonstrated that increasing activity in the ECN lowers perceived pain (27-29) and changes activity in nodes of the Salience Network (cingulate, insula) (30, 38, 39) which represent the attentional aspects of the pain network. One form of TMS is known as theta burst stimulation (TBS). **This biologically relevant pulse sequence, is translationally derived from preclinical studies in learning and memory, and has powerful effects on cortical excitability in humans (40), wherein the same LTP-like effects of 10 Hz TMS are achieved much faster with TBS.** As with traditional rTMS, TBS can induce LTP-like or LTD-like effects on by applying the pulses intermittently (iTBS, LTP-like) or continuously (cTBS, LTD-like) (40).

While the promise of inducing a lasting neuroplastic change in the Pain Network of opiate dependent individuals is enticing, it is not clear that the 'plasticity potential' of these circuits is as high in chronic opiate users as in healthy controls. Our preliminary data evaluating TMS to the DPFC as a tool for dampening pain circuitry is promising (Aim 1, Strategy 1). However, given previously observed deficits in executive function in chronic pain patients on chronic opiates (44), data has revealed that it may be more efficacious to attenuate activity in the MC (Aim 2, Strategy 2). The rationale for this alternative hypothesis is that in patients with chronic, ongoing pain, normal regulatory mechanism are disrupted (34-36). This alteration in brain function encourages the exploration of alternative treatment locations in this population.

**Early Feasibility Data: Quantitative Sensory Testing of pain in opiate using individuals after 10 sessions of rTMS (Strategy 1 and 2).** Our group recently initiated a 10 day clinical trial of these 2 strategies as tools to decrease behavioral reports of pain. From June 2017 to October 2017 we were able to enroll and successfully acquire Quantitative Sensory Testing data from 10 individuals (5 of whom

[figure not shown]

Figure 2. LTP-like DLPFC TMS is known to attenuate the Pain Network (Taylor et al 2013, and others). The LTD-like vmPFC TMS attenuates the ACC and Insula(Hanlon et al, under review) and is reciprocally related to the DLPFC (Dunlop et al 2016, and others).

received each strategy for 10 days). 8 of the 10 remained enrolled for the full treatment. The 2 that didn't finish were terminated due to a Hurricane in our area (Sept 2017). This initial feasibility trial is promising and individuals appear to be receiving pain relief (as demonstrated by their continued engagement). However, without a rigorous sham control group or longitudinal neuroimaging data, the results of this pilot study will be limited to Quantitative Sensory Testing. Through this R21 mechanism we hope to be able to build upon the early success of this trial by including a rigorous, randomized, sham-controlled design which includes neuroimaging data necessary to understand mechanisms of action of these innovative new treatment approaches.

*Aims 1 & 2 of this proposal will address the next critical steps in developing DPFC or MC TMS as a new, innovative treatment option for pain: 1) Do multiple sessions of rTMS have a sustainable impact on pain in CLBP patients? And 2) Are there consistent patterns of neural activity to pain that serve as a predictive biomarker for TMS efficacy in these individuals?*

**INNOVATION:** The proposed research is innovative in several ways. First, we are developing a conceptually innovative, alternative treatment strategy for chronic pain, which involves non-pharmacologic modulation of the circuits responsible for the perception of pain. This would be a significant conceptual advance for the field of chronic pain management. While LTP-like DPFC rTMS has been promising as a tool for pain in non-opiate dependent individuals, the experiments outlined in this proposal represent a critical next step in their development for this CLBP population chronically using opiates. The knowledge gained from these Aims would be the basis for further examination in a larger Clinical Trial of TMS (R01) and would hasten the pipeline through which TMS could be developed as an evidence-based neuromodulation strategy for physicians and pain management providers to offer to patients with chronic lower back pain. Second, while most TMS investigations focus on the relative efficacy of stimulation at a single site (or a single functional network), by evaluating 2 strategies in this proposal we will be uniquely positioned to advance the field. Third, we are using a novel stimulation profile, theta burst stimulation (TBS) that was supported by our preliminary data, and is built on a foundation from learning and memory literature in preclinical research. This stimulation profile will significantly reduce the total time of active stimulation relative to 10 Hz rTMS, thus reducing patient burden. Fourth, we are including a mixed population of individuals with CLBP, which includes individuals currently taking prescription opiates, and individuals not currently taking prescription opiates, which may provide evidence about the mechanisms of action of rTMS and its ability to decrease pain.

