### Inclusion Criteria

1. Age 18-75 (to maximize participation)
2. Can currently be using prescription opiates
3. Has current chronic back pain (> 3 months)
4. Able to read and understand questionnaires and informed consent.

Protocol version: 3.0

Protocol date: 07/14/2020

5. Is not at elevated risk of seizure (i.e., does not have a history of seizures, is not currently prescribed medications known to lower seizure threshold)
6. Does not have metal objects in the head/neck.
7. Does not have a history of traumatic brain injury, including a head injury that resulted in hospitalization, loss of consciousness for more than 10 minutes, or having ever been informed that they have an epidural, subdural, or subarachnoid hemorrhage.
8. Does not have a history of claustrophobia leading to significant clinical anxiety symptoms.

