### **Sample Size**

A power estimate for Aim 1 and 2 was prepared using an original fMRI dataset previously collected in our laboratory (8). In this experiment, 18 healthy controls performed the same fMRI pain paradigm as the present study before and after a single session of 10 Hz rTMS. Mean parameter estimates for the “heat pain vs. rest” condition were extracted from several *a priori* regions of interest. These data yielded an effect size which ranged from 0.70 (thalamus) to 1.08 (insula) (n=15 yields 80% power using a two-sided p<0.05). Allowing for a 10% dropout rate after the screening visit, and up to a 20% dropout rate at the end of the Treatment phase (Week 4), as well as a 10% data loss rate for MRI (Aim 2) due to individuals with excessive head motion in the MRI scanner, screening 58 individuals should lead to complete data from 48 individuals (16 real DPFC, 16 real MC, 16 sham (50% at each site)). Randomization will be handled by a Latin Square design with replacement will be used to ensure even enrollment across groups with replacement. All individuals will be enrolled at WFUHS. Data analysis and quality assessment will be ongoing.

Due to several COVID related factors, including challenges with scheduling and hesitation that participants may have wearing a mask in the MRI scanner, some participants will not receive the MRI

portion of this experiment. This will not affect our total enrollment goals, nor compromise the scientific integrity of this study. Moreover, it will lower the risk associated with MRIs to these participants.

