- C. Neuroimaging Data (Aim 2):** Immediately following acquisition, functional structural data will be uploaded to a secure data server and converted to NIfTI format. All preprocessing and analyses will be performed using Statistical Parametric Mapping 12 (SPM12) in Matlab 2013 (Mathworks). Functional data will be corrected for magnetic field inhomogeneity and realigned (rigid-body, minimizing least squares differences) to the first image in the time series (Realign: Estimate and Unwarp). Non-linear deformations required for standard space normalization will be derived from each participant's anatomical image via a unified segmentation approach (Segment). After the mean realigned and unwarped functional image is coregistered to the skull stripped anatomical image (Coreg: Estimate) forward deformations (subject space to MNI standard space) will be applied (Normalise: Write). Finally, the data will be smoothed by an 8 mm full width half maximum Gaussian smoothing kernel (Smooth). Within-subject and between-group modeling. Data will be analyzed at the subject level using multivariate pattern analysis (Wager et al 2013 “An fMRI-Based Neurologic Signature of Physical Pain” new England Journal of Medicine). The six motion parameters (translations and rotations) will be included in the design matrices as covariates to account for non-task signal.

Resting State Connectivity will be measured to compare MRI scan 1 to scan 2 – immediately after the treatment. MRI scan 3 will also be compared to these scans to see if there is a sustainable reduction in pain activity between these networks. Additionally factor analysis will be used to investigate the durability of the effects of each strategy on functional connectivity in each of the 3 Core networks (SN, ECN, DMN) using factor analysis longitudinally. **Covariates:** As an exploratory analysis we will also quantify the impact of several covariates which have previously been documented to affect the brain response to pain and pain thresholds (sex, Becks Depression Inventory score, length of time using chronic opiates). Although all participants will have taken their daily dose of opiates, which has a stable pharmacokinetic profile, we will also consider time since last dose.

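### Current opioid use is raised as a possible modifier of the TMS effect, but allocation is not stratified by it and the main models have no term for it

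*Combined protocol and SAP*

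**What the plan says.** **Population.** The Inclusion Criteria permit opioid use without requiring it ("Can currently be using prescription opiates"), and no quota or expected share of users is stated. The Innovation paragraph of the Background presents the mix as a strength, "we are including a mixed population of individuals with CLBP, which includes individuals currently taking prescription opiates, and individuals not currently taking prescription opiates", and adds that it may shed light on how rTMS works.

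**Opioid use and response.** The Background reports that naloxone blocks the analgesic effect of DPFC stimulation, "suggesting TMS-induced analgesia is opiate mediated". It then says it is unclear whether the plasticity "of these circuits is as high in chronic opiate users as in healthy controls". Expected (and alternative) Outcomes returns to this as a possibility: if the DPFC response is not replicated in opiate-dependent people, the motor-cortex target may prove the better one.

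**Allocation.** Sample Size gives the arms as "16 real DPFC, 16 real MC, 16 sham (50% at each site" and describes the method as follows: "Randomization will be handled by a Latin Square design with replacement will be used to ensure even enrollment across groups with replacement". Objectives and Design also refer to a Latin square. None of the three sections names a stratification factor.

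**Analysis.** Outcome Measure(s), items A and B, sets out repeated-measures models with time, treatment and no opioid-use term. Item C covers length of chronic opiate use under "As an exploratory analysis we will also quantify the impact of several covariates" and adds time since last dose. Expected Outcomes lists opiate dose and timing as potential covariates. The Quality Assurance Plan says baseline comparability will be examined and analyses adjusted where needed, without naming a variable or a rule.

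**The concern.** The plan gives a scientific reason why users and non-users might respond differently, and recruits both groups partly for that reason. Neither the allocation nor the main analysis then uses the factor. With 16 per arm, chance alone can leave arms with quite different proportions of users. If users and non-users change differently over the treatment weeks, part of an observed arm difference would reflect who was in the arm.

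The Outcome Measure(s) section says the trial exists to supply effect sizes for a later, larger study, so the accuracy of these single-trial estimates matters. An arm that happens to receive few users also says little about the mechanistic question. None of the listed covariates is simply current use, yes or no, and no specified analysis compares users with non-users.

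The covariates paragraph of item C also describes every participant as having taken a daily opiate dose. That does not fit a mixed cohort, and the two passages need to be reconciled.

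**Working it through.** **The plan's own figures.** The documents give no probability of opioid imbalance, so there is none to reproduce. The only sizing figure is n=15 for 80% power at two-sided 0.05, with effect sizes of 0.70 to 1.08. A two-sample t-test at 1.08 does need 15 per arm (power 81.5%). What is used here is the planned 16:16:16 split.

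**Inputs.**
- Arm size 16, total 48 (Sample Size).
- Allocation unrelated to opioid use (no factor named).
- Share of users p: not in the documents; assumed, range 20% to 70%.
- Event: a gap of at least 4 of 16, that is 25 percentage points, in either direction.

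**Chance of the gap.** Let the number of users in each arm be Binomial(16, p). For a sham count s, let a(s) be the probability that an active arm's count differs from s by 4 or more.
- One named active arm against sham: sum over s of P(s) × a(s).
- At least one of the two active arms: sum over s of P(s) × [1 − (1 − a(s))²].
- Pooled real (32) against sham (16): the same 25-point gap, with Binomial(32, p)/32 against Binomial(16, p)/16.

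| Share of users | One named active arm | At least one active arm | Pooled real |
|---|---|---|---|
| 20% | 0.119 | 0.206 | 0.054 |
| 30% | 0.175 | 0.296 | 0.094 |
| 40% | 0.206 | 0.342 | 0.118 |
| 50% | 0.215 | 0.357 | 0.126 |
| 60% | 0.206 | 0.342 | 0.118 |
| 70% | 0.175 | 0.296 | 0.094 |

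Fixing the total at 24 users of 48 (hypergeometric) gives nearly the same values: 0.220, 0.359 and 0.125.

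**Size of the shift.** Assume that users and non-users differ by 0.5 to 0.8 SD in change over time, whichever arm they are in. A 25-point gap then moves an unadjusted contrast by 0.25 × 0.5 = 0.125 SD to 0.25 × 0.8 = 0.20 SD. The standard error of a 16 against 16 contrast is √(2/16) = 0.35 SD, so the shift is 0.35 to 0.57 standard errors.

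**Arms with few users.** The chance that at least one arm has 3 or fewer users of 16 is 1 − [1 − P(X ≤ 3)]³. That is 57% if 30% are users, 18% at 40% and 3% at 50%.

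**After the fix.** With permuted blocks of 3 or 6 within opioid strata, 40,000 simulated trials at 50% users gave no gap of 25 points or more. An unfinished block of 6 leaves two arms at most 2 users apart, roughly 2/16 = 12.5 points.

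**Precision of the interaction.** With four cells of about 8, the standard error of arm × opioid use is √(4/8) = 0.71 SD. The 95% interval is about ±1.96 × 0.71 = ±1.4 SD.

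**The case against.** Five points on the other side deserve weight.

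**Strength of the claim about modification.** A reader might infer that the protocol expects opioid use to modify the effect, or treats it as the leading modifier. The documents do not support that. They call the matter unclear, possible, or something the mix may shed light on. The naloxone finding concerns how DPFC analgesia works; it does not say that prescription users respond differently, and it does not cover the motor-cortex arm. No modifiers are ranked, and gender is singled out for specific attention under Exploratory Analysis. This stands.

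**One in three.** A reader might take this as the chance of a serious imbalance. It holds only for a gap in either direction, in at least one of two comparisons, with roughly 30% to 70% users. One named arm gives about one in five at most. The pooled real against placebo grouping that items A and B actually state gives about one in eight. This stands too, although Exploratory Analysis compares each target with sham, so the per-arm figures remain relevant.

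**Repeated measures.** Stable differences in level between users and non-users cancel in a time by treatment analysis. Only a difference in change matters, and its size here is assumed. A pure modifier, moreover, acts through the make-up of the active arm rather than through the gap against sham. Both points are right and limit the harm.

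**Size.** Given a gap of exactly 4 of 16, a shift of 0.35 to 0.57 standard errors raises the false-positive chance from 5% to roughly 6% to 9% (normal approximation). Averaged over all allocations, randomisation keeps it at 5%. A reader might infer systematic bias; there is none.

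**Existing safeguards.** The Quality Assurance clause and the regression for outcome predictors in the Analytical Plan leave room to adjust. But neither names opioid use, and the adjustment clause operates after the data have been inspected. They make adjustment possible without specifying it.

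**Conclusion.** The point holds as a cheap improvement to a small trial. It is not a flaw that undermines the trial. The documents establish that no stratification by opioid use is named, that the main models have no opioid-use term, and that the opioid variables listed are exploratory or optional.

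The probabilities rest on an assumed user share and on allocation unrelated to opioid use. The 0.13 to 0.20 SD shift rests on an assumed difference in change over time and is smaller than one standard error. The effect is a chance imbalance and some loss of precision in estimates meant to inform a later trial. Stratifying would spread users evenly but would not make the mechanistic question answerable with 48 people, because the interaction estimate would remain very imprecise.

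**What to change.** - Stratify allocation by current prescription opioid use (yes/no), with small permuted blocks of 3 or 6 within each stratum.
- Pre-specify opioid use and its interaction with time in the main models. If enrolment has begun, add this covariate alone.
- Report the arm × opioid-use estimate with its confidence interval as exploratory, stating that at about 8 per cell the 95% interval is roughly ±1.4 SD.
- Reconcile the covariates paragraph of item C with the mixed population.

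**Cost.** One field in the allocation list, at most one incomplete block per stratum, and one or two model degrees of freedom for a before/after comparison (more if each visit enters as its own category). Opioid use is already assessed at screening, and dose and timing are recorded at each visit, so no new data collection is needed.
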